4.5 DOSE ESCALATION STOPPING RULES

The Medical Monitor will apply the following rules to determine if it is safe to proceed to the next Dose Level, or if dose escalation should stop. Pre-specified rules for pausing or stopping the whole study are described in Section 8.5 and rules for individual patient withdrawal are described in Section 8.4.

Should one of three patients in a Dose Level experience dose-limiting toxicity (DLT, see Section 8.1.2 for definition) within 7 days after receiving the first dose of the cells that is considered probably or definitely related to Descartes-30, 3 more patients will be enrolled and treated at that Dose Level. If only 1/6 of patients at that Dose Level has a DLT, and if the medical monitor agrees, treatment will proceed to the next higher Dose Level. If 2 or more out of 3 to 6 patients develop a DLT, no further patients will be dosed at that dose level. The MTD will be defined as the highest dose at which a maximum of 1 of 6 patients has a DLT. In Arm 2, up to 12 more patients who meet the eligibility criteria may be treated in each cohort (ARDS and PNA) at a dose up to MTD, provided that the medical monitor approves the enrollment of each such patient based on ongoing review of the cumulative safety data.

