8.1.2 DOSE LIMITING TOXICITY (DLT)

Following reactions within 4 hours of Descartes-30 infusion will be considered as DLT:

1. Addition of a third vasopressor
2. Increase in vasopressor dose over baseline greater than or equal to the following:
 - a. Norepinephrine: 1.5 μ g/kg per min
 - b. Phenylephrine: 100 μ g/kg per min
 - c. Dopamine: 10 μ g/kg per min
 - d. Epinephrine: 1 μ g/kg per min
 - e. Vasopressin: 0.04 IU/min
3. Hypoxemia requiring an increase over baseline in FiO_2 of ≥ 0.2 and/or increase in positive end-expiratory airway pressure level of 5 cm H₂O or more to maintain transcutaneous oxygen saturations in an acceptable range based on PI's discretion
4. New cardiac arrhythmia requiring cardioversion (chemical or electrical)
5. New ventricular tachycardia, ventricular fibrillation, or asystole
6. Death

Also, any Grade 3-5 toxicity probably or definitely attributed to Descartes-30 will be a DLT.

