8.2 RECORDING OF ADVERSE EVENTS

8.2.1 ADVERSE EVENT RECORDING

The adverse event recording period for this study starts after patient or legal representative signs consent and ends at Day 90 visit or when patient comes **off-study based on criteria in Section 8.4**. For SAE and SUSAR, reporting period starts with first Descartes-30 infusion and ends 7 days after last infusion. After 7 days, an AE (only in Arm 2), SAE (both Arms) or SUSAR (both Arms) is **only reported if it is probably or definitely attributed to Descartes-30 infusion**. At each contact with the subject during the adverse event recording period, the Investigator or his/her designee must seek information on adverse events by specific questioning and, as appropriate, by examination. Information on all adverse events should be recorded immediately in the source document, and in the appropriate adverse event module of the case report form (CRF). All clearly related signs, symptoms, and abnormal diagnostic procedures results should be recorded in the source document, though it should be grouped under one diagnosis.

All adverse events should be treated appropriately. If a concomitant medication or non-drug therapy is given, this action should be recorded on the Adverse Event CRF. Adverse events should be entered into the e-CRF system within 3 working days from the knowledge of the event took place. Once an adverse event is detected, it should be followed until its resolution or until it is judged to be permanent, and assessment should be made at each visit (or more frequently, if necessary) of any changes in severity, the suspected relationship to the study treatment, the interventions required to treat it, and the outcome.

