8.3 SAE AND SUSAR REPORTING

To ensure patient safety, every SAE and SUSAR, regardless of suspected causality, occurring during the adverse event reporting period defined in Section 8.2.1 must be reported to the Sponsor within 24 hours of learning of its occurrence. Recurrent episodes, complications, or progression of the initial SAE must be reported as follow-up information is received. An SAE occurring at a different time interval or otherwise considered completely unrelated to a previously reported one should be reported separately as a new event.

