8.5 STUDY PAUSING AND STOPPING RULES

Premature termination of the clinical trial may occur because of a regulatory authority decision, change in opinion of the IRB or Medical Monitor. Additionally, recruitment may be stopped for reasons of particularly low recruitment, protocol violations, or inadequate data recording. Specifically, study will be stopped if:

- Study Sponsor or a Regulatory Body decides for any reason that subject safety may be compromised by continuing the study.
- The Sponsor decides to discontinue the development of the intervention to be used in this study.

The study will be **paused if:**

- There is death that is reasonably attributed to study product before Day 4.
- Two subjects with Grade 3 or 4 adverse events to vital organs that are assessed as probably or definitely related to study product within the first 7 days after first infusion.

If the study is paused for the reasons above, the PI and members of the study team will meet in person or by teleconference within 24 hours of the event to have a thorough discussion of the event. Meeting minutes capturing the review of any ongoing investigations, including next steps in the management of the subject and any proposed changes to the protocol will be forwarded to the Medical Monitor. If all parties agree as to the event resolution, then the pause will be lifted. If the study is paused for manufacturing reasons, the Sponsor will make recommendations for process improvements to be implemented. Pending successful completion of a process validation run, the manufacturing pause will be lifted.

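### A related but non-serious Grade 3–4 organ toxicity counts toward the study pause yet has only a 3-working-day e-CRF deadline, so the 24-hour pause meeting is not guaranteed

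*Combined protocol and SAP*

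**What the plan says.** - **What counts as a DLT (8.1.2).** There are two limbs. The first is a list of acute reactions: "Following reactions within 4 hours of Descartes-30 infusion will be considered as DLT". The second is broader: "any Grade 3-5 toxicity probably or definitely attributed to Descartes-30 will be a DLT".
- **What pauses the study (8.5).** Apart from an early death attributed to the product, the trigger is "Two subjects with Grade 3 or 4 adverse events to vital organs that are assessed as probably or definitely related to study product", within 7 days of first infusion. Once the study is paused, "the PI and members of the study team will meet in person or by teleconference within 24 hours of the event". The minutes then go to the medical monitor.
- **What travels fast (8.3, 8.3.1).** An SAE or SUSAR "must be reported to the Sponsor within 24 hours of learning of its occurrence". The SAE list in 8.1.3 covers death, the 8.1.2 infusion reaction, prolonged hospitalization, incapacity and, at the investigator's or sponsor's judgment, important medical events.
- **What travels slowly (8.2.1).** For every other event, "Adverse events should be entered into the e-CRF system within 3 working days from the knowledge of the event took place". The same section also says: "Information on all adverse events should be recorded immediately in the source document, and in the appropriate adverse event module".
- **Who pools the information (10.3).** The medical monitor brings together safety information across sites and applies the stopping criteria.
- **Arm 2 (synopsis, 4.2, 4.4, 4.5, 6.4).** Up to 24 patients are enrolled consecutively. The 7-day interval between patients and the joint Day 7 review apply to Arm 1 only. Arm 2 patients may be treated "provided that the medical monitor approves the enrollment of each such patient based on ongoing review of the cumulative safety data".

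**The concern.** The pause rule counts events by grade, organ and attribution. The fast reporting route selects events by seriousness. The two sets overlap but are not the same, and the events in the gap are ones the pause rule exists to catch. A related Grade 3 rise in creatinine or liver enzymes in a patient already in hospital is a plausible example: it may not prolong the stay, and so may not be serious.

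The rule also needs two subjects in a multi-center trial. If one event occurs at each of two sites, neither investigator can be expected to know that the count has reached two. That depends on someone who sees all sites, and no stated deadline puts a non-serious qualifying event in front of that person within 24 hours.

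At stake is whether the pause works in Arm 2, where new patients can start without a waiting period.

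**Working it through.** The plan gives no figure to reproduce here. The check compares its stated clocks.

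**Step 1. Which pause-eligible events lack a 24-hour route?**

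| Related event within 7 days of first infusion | DLT? | Counts toward two-subject pause? | 24-hour report to sponsor? |
|---|---|---|---|
| Listed reaction within 4 hours of infusion | Yes | If Grade 3–4 and vital organ | Yes, an SAE by 8.1.3 |
| Grade 3–4, vital organ, prolongs the stay | Yes | Yes | Yes, an SAE by 8.1.3 |
| Grade 3–4, vital organ, judged an important medical event | Yes | Yes | Yes, but by judgment |
| Grade 3–4, vital organ, none of the above or another 8.1.3 criterion | Yes | Yes | **No; e-CRF within 3 working days** |
| Grade 3–4, not a vital organ | Yes | No | Only if serious |

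The fourth row is the gap. Grade 4 does not close it automatically: in 8.1.3, life-threatening appears only inside the discretionary clause and is not a criterion of its own.

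**Step 2. Three working days in calendar days.** Assumptions: Monday-to-Friday week, day of knowledge not counted, no public holiday.

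| Site learns on | Deadline | Calendar days | Hours beyond 24 |
|---|---|---|---|
| Mon | Thu | 3 | 72 − 24 = 48 |
| Tue | Fri | 3 | 48 |
| Wed | Mon | 5 | 120 − 24 = 96 |
| Thu | Tue | 5 | 96 |
| Fri | Wed | 5 | 96 |
| Sat | Wed | 4 | 96 − 24 = 72 |
| Sun | Wed | 3 | 48 |

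**Step 3. When must the sponsor know?** Let *t* be the hours from the event to site knowledge.

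- e-CRF route: *t* + 72 to *t* + 120 hours.
- SAE route: *t* + 24 hours.
- Meeting deadline in 8.5: 24 hours from the event, whatever *t* is.

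Even the SAE route does not secure the meeting, because reporting may use its full 24 hours and starts later whenever *t* > 0.

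**Step 4. What fits in the window?** Infusions on Days 0, 1 and 2 span about 48 hours from first to third. At the 12-hour minimum spacing in 6.2 the span is about 2 × 12 = 24 hours, ignoring infusion time. On the daily schedule, a patient first infused up to 72 − 48 = 24 hours after the site knew (3-day window), or up to 120 − 48 = 72 hours after (5-day window), could finish before the e-CRF deadline. Delays allowed under 7.1.2.1 would lengthen the course.

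**Step 5. How likely is a trigger?** The documents give no event rate. As an assumption, let each of 24 Arm 2 patients independently have a qualifying event, serious or not, with probability *p*. Then P(at least 2) = 1 − (1−*p*)^24 − 24*p*(1−*p*)^23, which is 0.083 at *p* = 0.02, 0.339 at 0.05 and 0.708 at 0.10. This is the chance of reaching the trigger, not of a delayed report or of harm.

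**The case against.** A reader might infer that the 24-hour meeting cannot be met, and that this affects all related Grade 3 toxicities. The documents do not support that.

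- Three working days is a ceiling, and 8.2.1 also asks for immediate recording.
- The meeting is of the PI and study team. They may already know of the event and need not wait for the sponsor to receive an e-CRF entry.
- Infusion reactions and events that prolong hospitalization already go by the 24-hour route, and others may by judgment.
- Only vital-organ events in the first 7 days count toward the pause, and two subjects are needed.

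All of this stands and limits the point to the fourth row of the first table.

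Three further defences are weaker.

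- **SUSAR route.** Section 8.1.4 defines unexpectedness without restating seriousness, so a site might report an unlisted Grade 3 event that way. But the category is headed as serious, and a pause rule should not depend on that reading.
- **Monitor approval of each Arm 2 patient (4.5).** This is a real gate, and nothing confines the monitor to e-CRF data. Equally, nothing requires a site to tell the monitor sooner. The gate also concerns enrolment; it does not mention the remaining infusions of patients already approved.
- **Discussion with the monitor under 7.1.2.1.** It is needed only to re-dose the affected patient before the toxicity has resolved far enough. It does not arise if that dose is simply delayed, or after the third infusion.

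**Conclusion.** The concern holds for a defined subset: probably or definitely related Grade 3–4 vital-organ events, within 7 days of first infusion, that are neither 8.1.2 infusion reactions nor otherwise serious under 8.1.3. For these, the permitted delay to the sponsor is 3 to 5 calendar days from knowledge. That is 48 to 96 hours more than the 24 hours allowed for the meeting, before adding any time from event to knowledge. The meeting is not guaranteed, least of all when the two subjects are at different sites. An Arm 2 patient could complete treatment before the event must be visible.

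This is a worst case under the written rules, not a forecast. It needs a non-serious qualifying event, entry near the deadline, no informal contact, and a patient starting or continuing in that window. The calendar figures assume an ordinary working week; a public holiday would lengthen them. The point is worth acting on because the gap lies in the study's own pause rule and is cheap to close.

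**What to change.** 1. **Sections 8.3 and 8.3.1.** Extend the existing notification, within 24 hours of awareness and to both sponsor and medical monitor, to every DLT under 8.1.2 and every probably or definitely related AE of Grade 3 or higher. Apply it in both arms, whether or not the event is serious.
2. **Section 8.5.** Start the 24-hour meeting clock when the sponsor becomes aware that a pause criterion is met.

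Together these cut the permitted delay to the sponsor from 72–120 hours to 24 hours after site knowledge. If the sponsor recognizes the trigger on receipt, the meeting falls within 24 + 24 = 48 hours of the site learning of the second qualifying event. Both changes are needed: the first alone leaves a meeting clock that starts before anyone may know of the event.

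The cost is a few extra 24-hour notifications by a route that already exists, and a meeting deadline that is nominally later than today's but can be met. No toxicity threshold or clinical rule changes. Confirmation from all sites before each Arm 2 enrolment is not needed; with the first change in place it would be largely redundant.

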9 STATISTICAL CONSIDERATIONS

9.1 SAMPLE SIZE

As this is an early-phase open-label study with a dose-escalation regimen, no formal sample size calculations have been performed. The sample size has been selected for practical considerations and is based upon experience from similar past clinical study designs. The selected number of subjects is considered sufficient to achieve the clinical study objectives, which are not of an inferential statistical nature.

9.2 SAFETY

The following safety parameters will be tabulated and analyzed descriptively: adverse events, clinical laboratory tests, ECGs, physical examinations, and vital signs. Dose escalation rule determination of MTD is described in Section 4.4.

[figure not shown]
9.3 EFFICACY

Efficacy will be assessed by descriptive statistics of treatment response per clinical endpoints that are frequently used in ARDS outcome trials such as all-cause mortality at Day 28, change in SOFA score from baseline, change in WHO Ordinal Score, change in PaO₂ / FiO₂ ratio (arterial partial pressure of O₂ / fraction of inspired O₂) from 0 to 96 hours after first dose, to determine all-cause mortality at Day 28 for patients diagnosed with COVID-19, change in PaO₂ / FiO₂ ratio from 0 to 24, 48, and 96 hours after first dose, days free of renal support (for patients receiving renal support at baseline), days free of vasoactive support (for patients receiving at least one vasopressor at baseline), days free of mechanical ventilation, days with a fever (temperature $\geq 38^{\circ}\text{C}$) number of ICU-free days, and number of days in hospital.

Days free of mechanical ventilation is defined as the number of calendar days during which the patient is ventilator-free including two unassisted breathing (UAB) days to Day 28, assuming that a patient survives for at least two consecutive calendar days after initiating UAB.

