6.5 SHORT-TERM FOLLOW-UP (DAY 14, 21 AND 28)

If patient is discharged from the hospital, Day 14 and 21 visits can be omitted. Day 28 visit can be the day of discharge from the hospital if it is earlier.

- Physical Exams: Only if patient is in the the administering unit, abbreviated, targeted physical examinations (i.e., assessments of the skin, respiratory, cardiovascular system, and abdomen (liver and spleen)), will be performed at time points specified in the Schedule of Activities (Section 1) and will be based on the subject's clinical status and what the clinic staff deem is appropriate.
- Concomitant medications
- Clinical End-point Assessment includes: Survival (Y/N), On mechanical ventilation (Y/N), In ICU (Y/N), In Hospital (Y/N), Use of anti-coagulation (drug, dose, intent: prophylaxis vs therapeutic), WHO Ordinal Score (See Appendix D for scale). If patient is in ICU then the following assessment will be completed: Sequential Organ Failure Assessment (SOFA), PaO₂/FiO₂, following ventilation parameters (as applicable): type of ventilation (CPAP, BiPAP, or intubation)/ ventilation rate/ pulse/ tidal volume/ positive end-expiratory pressure (PEEP), recording of vasoactive drugs and renal support, recording of supportive interventions that can impact clinical endpoints (use of prone ventilation, use of paralytics, use of pulmonary vasodilators, use of corticosteroids, use of oral decontamination and raising the head of the patient at least 30° to prevent ventilator-associated pneumonia)
- Vital Signs: include core temperature, mean arterial pressure (mmHg), pulse (beats/min), respiratory rate (breaths/min).
 - The same method for assessing temperature should be used at all visits for each individual subject, if possible.
- CBC with differential. Only if performed as Standard of Care.
- Serum chemistry. Only if performed as Standard of Care:

- Chemistry includes Glucose, Ca, Mg, Phos, ALP, Albumin, Total Protein, Total Bilirubin, K, Na, Cl, HCO₃, BUN, Cr, ALT, AST, LDH, Amylase.
- Chest Imaging: CT scan (preferred on Day 28) or Chest X-Ray. Only if performed as Standard of Care.
- AE review and evaluation
- Research blood collection: Only if patient is in the administering unit. All protocol required research blood collection assessments must be conducted in accordance with Laboratory Manual.

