6.6 LONG-TERM FOLLOW-UP (DAY 90± 14)

On Day 90± 14 days, an in-person visit, or telemedicine will be arranged to complete the assessments listed below. If any of the laboratory assessments cannot be performed due to inability to arrange a blood collection, it will not be considered as protocol deviation.

- Physical Exams: Abbreviated, targeted physical examinations (i.e., assessments of the skin, respiratory, cardiovascular system, and abdomen [liver and spleen]), will be performed at time points specified in the Schedule of Activities (Section 1) and will be based on the subject's clinical status and what the clinic staff deem is appropriate.
- Concomitant medications
- Clinical End-point Assessment includes: Survival (Y/N), On mechanical ventilation (Y/N), In ICU (Y/N), In Hospital (Y/N), Use of anti-coagulation (drug, dose, intent: prophylaxis vs therapeutic), WHO Ordinal Score (See Appendix D for scale). If patient is in ICU then the following assessment will be completed: Sequential Organ Failure Assessment (SOFA), PaO₂/FiO₂, following ventilation parameters (as applicable): type of ventilation (CPAP, BiPAP, or intubation)/ ventilation rate/ pulse/ tidal volume/ positive end-expiratory pressure (PEEP), recording of vasoactive drugs and renal support, recording of supportive interventions that can impact clinical endpoints (use of prone ventilation, use of paralytics, use of pulmonary vasodilators, use of corticosteroids, use of oral decontamination and raising the head of the patient at least 30° to prevent ventilator-associated pneumonia)
- Vital Signs: include core temperature, mean arterial pressure (mmHg), pulse (beats/min), respiratory rate (breaths/min).
- Research blood collection: Can be omitted if visit is telemedicine. All protocol required research blood collection assessments must be conducted in accordance with Laboratory Manual
- AE review and evaluation

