7.1.2.4 GUIDANCE FOR DISCONTINUATION OF MECHANICAL VENTILATION

The following weaning trial guidelines should be followed for patients who require mechanical ventilation at baseline or during the trial:

Patients should be assessed for the following weaning readiness criteria:

- PaO₂/FiO₂ >300 after 1 hour with PEEP <10 and FiO₂ <0.5
- Values of both PEEP and FiO₂ values are lower from previous day
- The patient is not receiving neuromuscular blocking agents
- The patient is exhibiting inspiratory efforts
- Systolic arterial pressure ≥ 90 mmHg without vasopressor support or minimal vasopressor support (i.e., ≤ 5 μ g/kg/min dopamine or dobutamine)

If these criteria are met, a spontaneous breathing trial (SBT) procedure and assessment for unassisted breathing should be performed. The SBT will take place for up to 120 minutes of spontaneous breathing with $\text{FiO}_2 < 0.5$ using any of the following approaches:

- Pressure support (PS) $\leq 5 \text{ cmH}_2\text{O}$, PEEP $\leq 5 \text{ cmH}_2\text{O}$
- Continuous positive airway pressure (CPAP) $\leq 5 \text{ cmH}_2\text{O}$
- T-piece
- Tracheotomy mask

If all criteria below are met for the last 30 minutes of the trial, the SBT will be reported as “successful” and ventilation support will be removed:

- $\text{SpO}_2 \geq 90\%$ and/or $\text{PaO}_2 \geq 60 \text{ mmHg}$
- Respiratory rate $\leq 35/\text{min}$
- No respiratory distress (defined as ≥ 2 of the following):
 - Heart rate $\geq 120\%$ of the rate at 06:00 ($\leq 5 \text{ min}$ at $\geq 120\%$ may be tolerated)
 - Marked use of accessory muscles
 - Abdominal paradox
 - Diaphoresis
 - Marked subjective dyspnea

If above criteria are not met, the SBT will be reported as “unsuccessful” and previous ventilator settings will be initiated. The patient should be reassessed for weaning the following day.

Patients will be reported as “ventilator free” after two consecutive calendar days of “unassisted breathing”. “Unassisted breathing” will be defined as any of the following:

- Spontaneously breathing with face mask, nasal cannula or room air
- T-piece breathing
- Tracheostomy mask breathing
- CPAP ≤ 5 without Pressure Support or intermittent mandatory ventilation assistance
- Use of CPAP or bi-level positive airway pressure solely for sleep apnea management

Please discuss with Sponsor if institutional ventilator weaning policy conflicts significantly with the above criteria.

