15 APPENDIX D

WHO Ordinal Score

The World Health Organization has endorsed the use of an ordinal scale as an outcome measure in clinical trials to capture the trajectory of patients' clinical progression and of healthcare resource use.⁵¹

Score	Descriptor
1	Discharged (alive)
2	Hospital admission, not requiring supplemental oxygen, no longer requiring medical care (hospitalisation extended for infection control or other nonmedical reasons e.g. social care. Sometimes documented as "medically fit for discharge" or "medically stable for discharge")
3	Hospital admission, not requiring supplemental oxygen, but requiring ongoing medical care
4	Hospital admission, requiring supplemental oxygen (by face mask or nasal prongs)
5	Hospital admission, requiring high flow nasal oxygen, continuous positive airways pressure or non-invasive ventilation
6	Hospital admission, requiring invasive mechanical ventilation or extracorporeal membrane oxygenation (ECMO)
7	Death

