16.4.4 DAY 28 (OR DAY OF DISCHARGE)

These assessments will be done on the day the patient leaves the hospital or on Day 28, whichever comes earlier.

- Concomitant medications
- Clinical End-point Assessment includes: Survival (Y/N), On mechanical ventilation (Y/N), In ICU (Y/N), In Hospital (Y/N), Use of anti-coagulation (drug, dose, intent: prophylaxis vs therapeutic), WHO Ordinal Score. If patient is in ICU then the following assessment will be completed: Sequential Organ Failure Assessment (SOFA), PaO₂/FiO₂, ventilation variables [type of ventilation (CPAP, BiPAP, or intubation), ventilation rate, pulse, tidal volume, positive end-expiratory pressure (PEEP)], recording of vasoactive drugs and renal support, recording of supportive interventions that can impact clinical end-points (use of prone ventilation, use of paralytics, use of pulmonary vasodilators, use of corticosteroids, use of oral decontamination and raising the head of the patient to at least 30° to prevent ventilator-associated pneumonia).
- Chest Imaging: CT scan (preferred) or Chest X-Ray.

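### Ventilator-free days in Section 9.3 keep their credit when a weaned patient later dies by Day 28, so a death can score above a late-weaned survivor

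*Combined protocol and SAP*

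**What the plan says.** Section 9.3 defines days free of mechanical ventilation in full and without redaction. It is a count of ventilator-free calendar days up to Day 28, with the two UAB days included. The only condition on survival is "assuming that a patient survives for at least two consecutive calendar days after initiating UAB".

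Section 7.1.2.4 calls a patient ventilator-free once UAB has lasted two calendar days in a row. It defines UAB by breathing status, for example "Spontaneously breathing with face mask, nasal cannula or room air". It does not mention death.

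Section 9.3 lists Day 28 all-cause mortality as a separate endpoint and says that efficacy is summarised descriptively. The primary endpoint in the synopsis is the maximum tolerated dose.

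On ascertainment, Section 6.5 says that the "Day 28 visit can be the day of discharge from the hospital if it is earlier". The Day 90 contact in Section 6.6 covers survival as a yes/no item: "Clinical End-point Assessment includes: Survival (Y/N), On mechanical ventilation (Y/N".

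**The concern.** A ventilator-free-day score is read as higher is better. The two-day condition screens out a patient who dies almost at once after coming off support. It does nothing about a patient who is weaned, stays off the ventilator for a while and dies in week two, three or four. That patient keeps every day credited before death.

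Two consequences follow. A patient who died inside the Day 28 window can have a better score than a patient who survived it. A group summary can also look more favourable when some of its credited days belong to patients who died. The Day 28 mortality line beside it gives the number of deaths, but not how many ventilator-free days those patients contributed.

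**Working it through.** The plan gives no expected ventilator-free days and, in Section 9.1, no sample-size calculation, so there is no stated figure to reproduce. The check scores the Section 9.3 rule directly.

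**Inputs**
- End of window: Day 28 (Section 9.3).
- Survival condition: two calendar days after UAB starts (Section 9.3).
- Cohort size: 12 per Arm 2 cohort (synopsis and Section 4.2).
- Days of weaning and death: assumed for illustration, with no return to ventilation.

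**Formulas**
- Death on day D after UAB from day s: days s to D − 1 are credited, so the score is D − s. Stopping at the day before death follows from Section 7.1.2.4, where UAB is a breathing status.
- Survivor to Day 28 with UAB from day u: days u to 28 are credited, so the score is 28 − u + 1 = 29 − u.

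**One death against survivors**
- UAB from Day 5, death on Day 20: 20 − 5 = **15**. The survival condition is met whether or not the start day counts as one of the two days.
- Survivor with UAB from Day 20: 29 − 20 = **9**.
- Survivor never liberated: **0**.
- The death outscores a survivor when 29 − u < 15, that is, for any survivor first unassisted on Day 15 or later.

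**Sensitivity to the counting convention**
- Counting the day of death gives 16.
- Reading the window as running to Day 28 regardless of death gives 29 − 5 = 24.
- Both alternatives widen the gap over the survivor's 9.

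**Effect on a cohort mean**
- Scoring this death as 0 instead of 15 moves the mean of 12 contributing patients by 15/12 = **1.25 days**.

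**Two assumed cohorts of 12**, each with eight survivors unassisted from Day 10 (29 − 10 = 19 days each, total 152):

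| Other four patients | Mean under Section 9.3 | Mean with death scored 0 |
|---|---|---|
| Died on Day 20, UAB from Day 4 (16 each) | (152 + 64)/12 = 18.0 | 152/12 = 12.7 |
| Survived, UAB from Day 20 (9 each) | (152 + 36)/12 = 15.7 | 15.7 |

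Under the rule as written, the cohort with four deaths has the better mean. With death scored 0, the order reverses.

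**The case against.** The best defence is that this is a choice of estimand. Days alive and off the ventilator, reported next to Day 28 mortality, is a coherent descriptive pair. Zero for death is common but not the only option; a worst rank would also work. Section 9.3 ranks no one and does not name the mean as its summary, and dose decisions rest on dose-limiting toxicity. Synopsis, objective and Section 16.5.2 text is redacted, so a rule on death could sit there.

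Much of this stands, and it limits the severity. It does not remove the problem. The definition in Section 9.3 is unredacted and reads as complete. It already contains a survival condition, so a reader will take death as dealt with when only the earliest deaths are. Separate mortality cannot show which credited days belong to patients who died.

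Three stronger readings are tempting but not supported:

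- **A contradiction with the WHO Ordinal Score**, which places death (7) below invasive ventilation (6). Two endpoints that measure different things may order patients differently. Section 9.3 also gives no time point for the change in WHO score.
- **A count of weaning-and-death patterns as evidence of frequency.** The number depends on conventions the plan does not fix: 351 if UAB starts on Day 1 or later and the start day counts towards the two, 378 if Day 0 is allowed, 325 if both survival days must follow a start on Day 1 or later. None of these is a probability.
- **The same error in ICU-free, renal-support-free and vasoactive-free days.** Section 9.3 only names these, and their definitions may be in redacted text.

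**Conclusion.** The point holds. As written, Section 9.3 lets a patient who dies by Day 28 score more ventilator-free days than a late-weaned survivor: 15 against 9 in the worked example, and 0 for a survivor never liberated. The direction does not depend on how the day of death is counted.

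The 1.25-day shift assumes one such death, that all 12 patients of a cohort contribute a score, and that the mean is reported. The second assumption may fail, because invasive ventilation is not required for entry and Section 9.3 does not say how never-ventilated patients are counted. How often death follows weaning is not given.

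The effect is moderate. The endpoint is descriptive and non-primary, mortality is reported beside it, and no error rate or dose decision depends on it. A reader might infer that the flaw already enters a hypothesis test, because Section 16.5.1 plans one-sided t-tests against parallel controls for continuous variables. Redaction in Section 16.5.2 leaves open whether ventilator-free days are among them, so this can be stated only as a condition that would make the point more serious.

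**What to change.** Add one sentence to Section 9.3: a patient who dies on or before Day 28 scores 0 ventilator-free days, whatever time was spent unassisted before death.

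For patients who leave hospital before Day 28, take Day 28 vital status from the Day 90 contact and record the date of death. A yes/no answer at Day 90 cannot place a death before or after Day 28. The Day 28 mortality endpoint already needs this information. Serious-adverse-event reports will not reliably supply it: under Section 8.2.1, from 7 days after the last infusion they are limited to events probably or definitely attributed to the product. The case report form is not in the documents, so the sponsor should check whether it already holds a date of death.

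If the score is compared with the Appendix E controls, use the same limit of ascertainment in both groups. For the controls, Section 16.4.4 sets the last assessment: "These assessments will be done on the day the patient leaves the hospital or on Day 28, whichever comes earlier".

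The cost is one sentence and at most one data field, with no added visit. Reported means become slightly less favourable. Deaths will tie at 0 with survivors never liberated; the separately reported mortality distinguishes them.
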